10.4 Subject Data Protection

The ICF(s) will incorporate or, in some cases, be accompanied by a separate document incorporating wording that complies with relevant data protection and privacy legislation. R-Pharm or R-Pharm's designee will not provide individual results to subjects, any insurance company, any employer, their family members, general physician or any other third party, unless required to do so by law.

Information about study subjects will be kept confidential and managed according to the regulatory requirements.

11.2 Study and Study Site Closure

Upon completion of the study, the monitor will conduct the following activities in conjunction with the Investigator or study site staff, as appropriate, including the following:

- Return of all study data to R-Pharm.
- Resolution of data queries.
- Accountability, reconciliation, and arrangements for unused study treatment.
- Review of study site, study records for completeness.
- Review requirements for record retention and audit responsibilities.

11.3 Study Discontinuation

The study may be discontinued at any time by the IRB/IEC, R-Pharm, or regulatory agencies as part of their duties to ensure that research subjects are protected.

R-Pharm reserves the right to temporarily suspend or prematurely discontinue this study either at a single study site or at all study sites at any time for reasons including safety or ethical issues or severe non-compliance. If R-Pharm determines such action is needed, R-Pharm will discuss this with the Investigator (including the reasons for taking such action) at that time. When feasible, R-Pharm will provide advance notification to the Investigator of the impending action prior to its taking effect.

R-Pharm will promptly inform all other Investigators and/or institutions conducting the study if the study is suspended or terminated for safety reasons, and will also inform the regulatory authorities of the suspension or termination of the study and the reason(s) for the action. If

required by applicable regulations, the Investigator must inform the IRB/IEC promptly and provide the reason for the suspension or termination.

If the study is prematurely discontinued, all study data must be returned to R-Pharm or its designee. In addition, arrangements will be made for return of all unused study treatment in accordance with R-Pharm's applicable procedures for the study.

Financial compensation to Investigators and/or institutions will be in accordance with the agreement established between the Investigator and R-Pharm.

11.4 Data Handling and Record Keeping

Information about study subjects will be kept confidential and managed according to the regulatory requirements. It is the Investigator's responsibility to maintain essential study documents (protocol and protocol amendments, completed eCRFs, signed ICFs, relevant correspondence, and all other supporting documentation). The study site should plan on retaining such documents for approximately 15 years after study completion. The study site should retain such documents until at least 2 years after the last approval of a marketing application in an ICH region and until there are no pending or contemplated marketing applications in an ICH region or at least 2 years after the formal discontinuation of clinical development of the study treatment. These documents should be retained for a longer period if required by the applicable regulatory requirements or the hospital, institution, or private practice in which the study is being conducted.

Subject identification codes (subject names and corresponding study numbers) will be retained for this same period of time. These documents may be transferred to another responsible party, acceptable to R-Pharm, who agrees to abide by the retention policies. Written notification of transfer must be submitted to R-Pharm. The Investigator must contact R-Pharm prior to disposing of any study records.

No records should be disposed of without the written approval of R-Pharm.

11.5 Direct Access to Source Data/Documents

The Investigator will prepare and maintain adequate and accurate source documents to record all observations and other pertinent data for each subject randomized into the study.

Source data is all information, original records of clinical findings, observations, or other activities in a clinical study necessary for the complete reconstruction and evaluation of the study. Source data are contained in source documents. Examples of these source documents and data records include: hospital records, clinical and office charts, laboratory notes, memoranda, subject's evaluation checklists, pharmacy dispensing records, recorded data

from automated instruments, copies or transcriptions certified after verification as being accurate and complete, microfiches, photographic negatives, microfilm or magnetic media, radiographs, subject's records, and records kept at the pharmacy, at the laboratories, and at medico-technical departments involved in the clinical study.

The Investigator will allow the authorized R-Pharm's designee and authorized regulatory authorities and IRBs/IECs to have direct access to all documents pertaining to the study, including individual Subject medical records, as appropriate.

11.6 Investigator Information

11.6.1 Investigator Obligations

The Investigator is responsible for ensuring that all study site staff, including sub-Investigators, adhere to all applicable regulations and guidelines, including local laws and regulations, regarding clinical studies both during and after study completion.

The Investigator is responsible for informing the IRB/IEC of the progress of the study, for obtaining annual IRB/IEC renewal, and informing the IRB/IEC of completion of the study, and will provide the IRB/IEC with a summary of the results of the study.

The study will be conducted in compliance with the protocol, GCP and the applicable regulatory requirements of European Commission Directive (2001/20/EC Apr 2001) and/or European Commission Directive (2005/28/EC Apr 2005) and/or US Food and Drug Administration GCP Regulations: Code of Federal Regulations Title 21, parts 11, 50, 54, 56, and 312, and/or other applicable local or regional regulations.

The Investigator agrees to conduct the clinical study in compliance with this protocol after the approval of the protocol by the IRB/IEC in compliance with local regulatory requirements. The Investigator and R-Pharm will sign the protocol to confirm this agreement.

11.6.2 Protocol Signatures

After reading the protocol, each Investigator will sign the protocol signature page and send a copy of the signed page to R-Pharm or its designee. By signing the protocol, the Investigator confirms in writing that he/she has read, understands and will strictly adhere to the study protocol and will conduct the study in accordance with ICH Tripartite Guidelines for GCP and applicable regulatory requirements. The study will not be able to start at any site where the Investigator has not signed the protocol.

11.6.3 Publication Policy

R-Pharm shall retain the title and the right to publish all documentation, records, raw data, specimens or other work product generated pertaining to the study (“data”) conducted by the study site (site includes the Investigator and the institution) as defined in the applicable protocol or study plan or study agreement. The study site shall maintain confidentiality and not disclose or divulge such “Data” to any third party. However, the study site may seek permission to publish such “Data” for limited purpose and such “Data” may be published by the study site only upon receipt of prior written approval from R-Pharm.

11.7 Financing and Insurance

R-Pharm is the Sponsor of the study. R-Pharm will provide insurance in accordance with local guidelines and requirements as a minimum for the subjects participating in this study. The terms of the insurance will be kept in the study files.

R-Pharm has obtained liability insurance, which covers this study as required by local law and/or national regulations and/or ICH guidelines, whichever is applicable. The terms of the insurance will be kept in the study files.

13. APPENDICES

13.1 Appendix 1: Steinbrocker Functional Classification

Table 1. Classification of functional capacity in rheumatoid arthritis*

Class I	Complete functional capacity with ability to carry on all usual duties without handicaps
Class II	Functional capacity adequate to conduct normal activities despite handicap of discomfort or limited mobility of one or more joints
Class III	Functional capacity adequate to perform only few or none of the duties of usual occupation or of self-care
Class IV	Largely or wholly incapacitated with patient bedridden or confined to wheelchair, permitting little or no self-care

* Steinbrocker criteria; reprinted, with permission, from *Journal of the American Medical Association* (1).

13.2 Appendix 2: New York Heart Association Functional Capacity Classifications

- Class I. Patients with cardiac disease but without resulting limitation of physical activity. Ordinary physical activity does not cause undue fatigue, palpitation, dyspnea, or anginal pain.
- Class II. Patients with cardiac disease resulting in slight limitation of physical activity. They are comfortable at rest. Ordinary physical activity results in fatigue, palpitation, dyspnea, or anginal pain.
- Class III. Patients with cardiac disease resulting in marked limitation of physical activity. They are comfortable at rest. Less than ordinary activity causes fatigue, palpitation, dyspnea, or anginal pain.
- Class IV. Patients with cardiac disease resulting in inability to carry on any physical activity without discomfort. Symptoms of heart failure or the anginal syndrome may be present even at rest. If any physical activity is undertaken, discomfort is increased.

13.3 Appendix 3: American College of Rheumatology 2010 Criteria

	Score
Target population (Who should be tested?): Patients who	
1) have at least 1 joint with definite clinical synovitis (swelling)	
2) with the synovitis not better explained by another disease	
Classification criteria for RA (score-based algorithm: add score of categories A–D; a score of $\geq 6/10$ is needed for classification of a patient as having definite RA)	
A. Joint involvement	
1 large joint	0
2–10 large joints	1
1–3 small joints (with or without involvement of large joints)	2
4–10 small joints (with or without involvement of large joints)	3
>10 joints (at least 1 small joint)	5
B. Serology (at least 1 test result is needed for classification)	
Negative RF and negative anti-CCP	0
Low-positive RF or low-positive anti-CCP	2
High-positive RF or high-positive anti-CCP	3
C. Acute-phase reactants (at least 1 test result is needed for classification)	
Normal CRP and normal ESR	0
Abnormal CRP or abnormal ESR	1
D. Duration of symptoms	
<6 Weeks	0
≥ 6 Weeks	1

Abbreviations: anti-CCP = anti-citrullinated protein antibody; CRP = C-reactive protein; ESR = erythrocyte sedimentation rate; RA = rheumatoid arthritis; RF = rheumatoid factor.

13.4 Appendix 4: Methotrexate Dose Reduction Guidelines

ALT and/or AST	Total Bilirubin	Repeat Laboratory	MTX	Study Treatment
1× to ≤2× ULN	<2× ULN	No need	No change	No change
>2× to ≤3× ULN	<2× ULN	Within 1 week	No change or can consider reduction in dose	No change
If repeat >2× to ≤3× ULN	<2× ULN	Within 1 week	Reduce dosage and follow LFTs	No change
>3× to ≤8× ULN (without the appearance of fatigue, nausea, vomiting, right upper quadrant pain or tenderness, fever, or rash)	≤2× ULN	Within 72 hours of initial finding, and then at least weekly after last finding until resolution, stabilization, or return to baseline values	Hold MTX until LFTs normalize or return to baseline and consider restarting at lower dose	No change
If repeat >3× to ≤8× ULN (without the appearance of fatigue, nausea, vomiting, right upper quadrant pain or tenderness, fever, or rash)	≤2× ULN	Within 72 hours of initial finding, and then at least weekly after last finding until resolution, stabilization, or return to baseline values	Hold MTX until LFTs normalize or return to baseline and consider restarting at lower dose	Hold and consider restarting after discussion with the R-Pharm Medical Advisor or designee
>3× ULN with appearance of fatigue, nausea, vomiting, right upper quadrant pain or tenderness, fever, rash, and/or eosinophilia (>5%)	≤2× ULN	Within 72 hours of initial finding, and then at least weekly after last finding until resolution, stabilization, or return to baseline values	Hold MTX. Follow local Standard of Care.	Permanently discontinue study treatment
>3× ULN	>2× ULN	Within 72 hours of initial finding, and then at least weekly after last finding until resolution, stabilization, or return to baseline values	Hold MTX. Follow local Standard of Care.	Permanently discontinue study treatment
>5× ULN for more than 2 weeks	≤2× ULN	Within 72 hours of initial finding, and then at least weekly after last finding until resolution, stabilization, or return to baseline values	Hold MTX. Follow local Standard of Care.	Permanently discontinue study treatment

R-Pharm
 CL04041022: Clinical Rheumatoid Arthritis Development for Olokizumab (CREDO) 1
 Olokizumab

ALT and/or AST	Total Bilirubin	Repeat Laboratory	MTX	Study Treatment
>8× ULN	≤2× ULN	Within 72 hours of initial finding, and then at least weekly after last finding until resolution, stabilization, or return to baseline values	Hold MTX. Follow local Standard of Care.	Permanently discontinue study treatment

Abbreviations: ALT = alanine aminotransferase; AST = aspartate aminotransferase; MTX = methotrexate; LFT = liver function test; ULN = upper limit of normal.

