6.11.1 Temporary Discontinuation of Study Treatment

The following laboratory abnormalities require prompt retesting following the reporting of the initial abnormal result (within 72 hours for abnormal LFTs and within 5 days for all other abnormal results):

- Any single ALT and/or AST elevation $>3 \times$ ULN, regardless of total bilirubin (repeat laboratory testing must include total bilirubin, direct and indirect bilirubin, gamma-glutamyl transferase [GGT], INR, alkaline phosphatase, creatine phosphokinase, and hematology assessment)
- Neutrophil count $<1000 \times 10^6/L$ ($<1000 /\text{mm}^3$)
- Lymphocyte count $<500 \times 10^6/L$ ($<500 /\text{mm}^3$)
- Platelet count $<100,000$ platelets/ mm^3
- Any single hemoglobin value <8.0 g/dL or one that drops ≥ 20 g/L (2 g/dL) below baseline

The next dose of study treatment will be held/interrupted if:

- Results from the repeat laboratory testing are not available at the time of the next scheduled dose
- ALT and/or AST remain $>3 \times$ ULN with total bilirubin $\leq 2 \times$ ULN after repeat laboratory testing and there are no symptoms consistent with hepatic injury (fatigue, nausea, vomiting, right upper quadrant pain or tenderness, fever, or rash). The Investigator may consider restarting study treatment only after discussion with the R-Pharm Medical Advisor or designee (see also Appendix 4 [Section 13.4]).

Clinically significant laboratory abnormalities should be re-tested and followed until resolution, stabilization, or return to baseline values, and the Investigator should contact the Medical Monitor for guidance regarding restarting the study treatment.

Study treatment should not be administered to subjects with active or clinically significant infections.

Temporary interruption of study treatment should also be considered if, at the discretion of the Investigator, it is necessary for safety reasons (e.g., negative trends during laboratory monitoring or remaining abnormalities after retesting which do not require premature discontinuation of the study treatment but could be harmful for the patient according to the Investigator's judgement, or other clinically significant newly diagnosed co-morbidity that

requires additional assessments for clarification of the diagnosis, and the severity of which could worsen if study treatment is continued).

The Investigator should contact the Medical Monitor for guidance regarding restarting study treatment.

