6.11.2 Permanent Discontinuation of Study Treatment

The criteria for enrollment are to be followed explicitly.

If a subject who does not meet enrollment criteria is inadvertently enrolled, R-Pharm or R-Pharm's designee must be informed immediately and the subject must immediately and permanently discontinue study treatment.

If, in the opinion of the Investigator, a subject is consistently noncompliant with the protocol in regards to study procedures, use of concomitant medications, or dosing with the study treatment, the case will be reviewed by R-Pharm on a case-by-case basis and noncompliant subjects can be discontinued from study treatment.

If the Investigator judges that the subject's health is deteriorating or not improving, the Investigator can elect to discontinue the subject from the study treatment. Appropriate standard of care, at the discretion of the Investigator, will be initiated.

In addition to the above, study treatment will be permanently discontinued in the following circumstances:

- Investigator decides that the subject should be discontinued from study treatment. If this decision is made because of an intolerable AE or a clinically significant laboratory value, the study treatment is to be discontinued, appropriate measures are to be taken, and R-Pharm or R-Pharm's designee is to be notified.
- Subject is unwilling to continue the study treatment. If the subject discontinues from the study treatment, the Investigator should inquire about the reason for discontinuing.
- Subject presents with any of the following elevated LFTs (see also Appendix 4 [Section 13.4]):
 - ALT or AST elevations $>8 \times$ ULN at any time, regardless of total bilirubin or accompanying symptoms
 - ALT or AST $>5 \times$ ULN for ≥ 2 weeks regardless of total bilirubin or accompanying symptoms
 - ALT or AST elevations $>3 \times$ ULN and total bilirubin value $>2 \times$ ULN

- ALT or AST elevations $>3 \times$ ULN accompanied by symptoms consistent with hepatic injury (fatigue, nausea, vomiting, right upper quadrant pain or tenderness, fever, or rash)
- Subject presents with any of the following laboratory abnormalities:
 - Absolute neutrophil count $<500 \times 10^6/L$ ($<500 /\text{mm}^3$)
 - Two sequential lymphocyte counts $<500 \times 10^6/L$ ($<500 /\text{mm}^3$)
 - Platelet count $<50 \times 10^9/L$ ($<50,000 /\text{mm}^3$ or $<50,000 \times 10^6/L$)
 - Two sequential hemoglobin values ≤ 8.0 g/dL and decreased ≥ 20 g/L (2 g/dL) below Screening value

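### Appendix 4 gives two incompatible study-treatment instructions for ALT/AST >3x to ≤8x ULN with new eosinophilia and no listed symptom, and no text says which governs

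*Combined protocol and SAP*

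**What the plan says.** Although titled as methotrexate guidance, Appendix 4 (Section 13.4) has a study-treatment column. Three of its rows matter here, all at total bilirubin ≤2x ULN.

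- Initial elevation: ">3× to ≤8× ULN (without the appearance of fatigue, nausea, vomiting, right upper quadrant pain or tenderness, fever, or rash". Study treatment: no change.
- Repeat finding, same range and same symptom exclusion. Study treatment: "Hold and consider restarting after discussion with the R-Pharm Medical Advisor or designee".
- The next row: ">3× ULN with appearance of fatigue, nausea, vomiting, right upper quadrant pain or tenderness, fever, rash, and/or eosinophilia (>5" (the threshold being 5%). Study treatment: permanent discontinuation.

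The body text carries the matching rules. Section 6.11.1 holds the next dose if ALT/AST stays above 3x ULN with bilirubin ≤2x ULN on retest and "there are no symptoms consistent with hepatic injury (fatigue, nausea, vomiting, right upper quadrant pain or tenderness, fever, or rash". On resuming, it says: "The Investigator may consider restarting study treatment only after discussion with the R-Pharm Medical Advisor or designee". It also holds the dose if "Results from the repeat laboratory testing are not available at the time of the next scheduled dose". Section 6.11.2 requires a permanent stop for ALT/AST above 3x ULN "accompanied by symptoms consistent with hepatic injury (fatigue, nausea, vomiting, right upper quadrant pain or tenderness, fever, or rash". Both sections refer the reader to Appendix 4. Neither mentions eosinophils.

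**The concern.** A hepatic stopping rule should give one answer for one set of results. Here the permanent-stop row adds eosinophilia as a sufficient feature in its own right, through the words *and/or*. The rows meant for uncomplicated elevations were not amended to exclude it.

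What is at stake is whether such a subject may ever be dosed again. One row forbids it; the others allow treatment to continue, or to restart after a hold. The choice also reaches the efficacy data. Under Section 9.4.9.1, a subject who does not remain on randomized treatment through the time point is a treatment failure in the main analysis of every binary endpoint. Two sites reading different rows could therefore record different ACR20 outcomes for the same clinical picture.

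**Working it through.** No arithmetic applies to the main point. The check is to take one defined case and test it against each rule's entry condition.

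Test case: ALT or AST >3x to ≤8x ULN, total bilirubin ≤2x ULN, none of the six listed symptoms, eosinophils newly above 5%, and not yet above 5x ULN for two weeks.

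| Rule | Is eosinophilia named? | Does the case meet it? | Study treatment |
|---|---|---|---|
| Appendix 4, initial elevation, symptom-free | No | Yes | No change |
| Appendix 4, repeat, symptom-free | No | Yes, if the elevation persists | Hold, restart possible |
| Appendix 4, symptoms and/or eosinophilia | Yes | Yes, at either finding | Permanent stop |
| 6.11.1 hold rule | No | Yes, if the elevation persists | Hold, restart possible |
| 6.11.2 symptom criterion | No | No | No stop required by this item |

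So two Appendix 4 rows apply at the initial elevation, and two at the repeat. Each time their study-treatment actions are incompatible.

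**Can the case arise and be seen?** Hematology includes a white-cell differential (Table 1 notes; Section 7.6.6.1). Chemistry and hematology are drawn together at Weeks 1, 4, 8, 12, 16 and 20. That makes six scheduled post-dose visits with a dose still to come, since the last dose is at Week 22. The retest required within 72 hours of a value above 3x ULN must itself include hematology (6.11.1, 7.6.3.4). A baseline hematology sample is taken at Week 0, so new eosinophilia can be told from old.

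**What follows in each branch?**

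- *Elevation persists on retest.* 6.11.1 holds the next dose whichever Appendix 4 row is preferred. The dispute is confined to whether restart is open.
- *Retest pending at the next dose.* 6.11.1 again holds the dose.
- *Retest ≤3x ULN and available in time.* Neither of these two 6.11.1 hold conditions is met. A site following the symptom-free row goes on dosing; a site following the eosinophilia row has already stopped for good. From the post-dose samples above, the next planned dose falls 1 week later (Week 1 to Week 2) or 2 weeks later (for example Week 4 to Week 6), so a 72-hour retest could be back in time.

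**Is there a hint about precedence?** Appendix 4 has another overlap. A symptom-free subject at 6x ULN for three weeks with bilirubin ≤2x ULN meets both the repeat row (hold) and the row for more than 5x ULN lasting over two weeks (permanent stop). There 6.11.2 settles the matter: it requires the stop when the elevation lasts 2 or more "weeks regardless of total bilirubin or accompanying symptoms". The eosinophilia overlap has no such confirming line.

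**The case against.** The strongest reply is that the table is an escalation ladder, in which a row with an added aggravating feature overrides the plainer row. The overlap above 5x ULN works that way. Because 6.11.2 points to Appendix 4, the appendix can be read as adding a criterion to the body text, not contradicting it. This makes the permanent stop the likelier intent. It does not remove the problem, because precedence has to be inferred and 6.11.2 does not confirm it for eosinophilia.

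The existing safeguards also stand. Methotrexate is held in all three competing rows, and the retest schedule is the same. The Investigator may interrupt or stop treatment for safety at any time.

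Several stronger readings are tempting and go too far.

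- *Sites may re-dose such subjects on their own judgement.* After a persistent elevation, restart requires discussion with the sponsor's Medical Advisor or designee. The weakness is that the table consulted in that discussion gives two answers.
- *Dosing will continue after a falling retest.* That happens only if the site takes the lenient row.
- *Any eosinophil value above 5% triggers the conflict.* The stop row speaks of *appearance*, which suggests new onset, so long-standing eosinophilia is not clearly covered.
- *The SAE criteria in 7.6.2 and 7.6.3.4 are wrong because they omit eosinophilia.* Those are reporting criteria and need not match a dosing rule.

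**Conclusion.** The overlap is real and shows on a plain reading of Appendix 4. For the defined case, two rows apply at each finding with incompatible study-treatment actions, and nothing states which prevails. The likelier intent is that the stop governs, so this is a drafting fault in a safety rule that should be corrected; it is not evidence that subjects are left unprotected.

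Its reach is small. Values above 8x ULN, values above 5x ULN for two weeks or more, bilirubin above 2x ULN together with ALT/AST above 3x ULN, and any of the six symptoms at that level all lead to a mandatory stop under 6.11.2 anyway. What remains is possible restart after a hold, or continued dosing when the retest falls to ≤3x ULN before the next dose. The documents do not allow the number of such subjects to be estimated. A reader might infer a material effect on the ACR20 comparison, but nothing in the plan supports that.

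The conclusion assumes that *and/or* makes eosinophilia sufficient alone, that 5% refers to the differential white-cell count, and that *appearance* applies to eosinophilia as it does to the symptoms.

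**What to change.** Make the permanent stop govern, in three places:

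1. In Appendix 4, add *or new eosinophilia (>5%)* to the exclusion lists of both >3x to ≤8x ULN rows.
2. In 6.11.1, add the same words to the no-symptoms condition of the hold rule.
3. In 6.11.2, add them to the criterion for ALT/AST above 3x ULN with symptoms.

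The test case then meets the stop row and the amended 6.11.2 criterion, and no other study-treatment instruction competes. If the sponsor never meant eosinophilia alone to end treatment, deleting it from the stop row would also give one answer. That is a clinical decision, and it goes against the likelier intent.

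The change is to wording only: no new visits, tests or subjects. The downside is a rare extra permanent discontinuation, which counts as non-response in the main binary analyses from that point on.

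As an optional tidy-up, Appendix 4 says more than 2 weeks for the rule above 5x ULN, where 6.11.2 says 2 weeks or more. The two differ only at exactly two weeks, when 6.11.2 already requires the stop; aligning the appendix would remove the mismatch.
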